5.4.3. Corrected QT Interval (QTc) Stopping Criteria

- The *same* QT correction formula *must* be used for *each individual subject* to determine eligibility for and withdrawal from the study. This formula may not be changed or substituted once the subject has been enrolled.
 - For example, if a subject is eligible for the protocol based on QTcB, then QTcB must be used for withdrawal of this individual subject as well.
 - Once the QT correction formula has been chosen for a subject's eligibility, the *same formula* must continue to be used for that subject *for all QTc data being collected for data analysis*. Safety electrocardiograms (ECGs) and other non-protocol specified ECGs are an exception.

- The QTc stopping criteria should be based on averaged QTc values of triplicate electrocardiograms obtained over a brief (e.g., 5-10 minute) recording period.

A subject who meets either of the bulleted criteria below will be permanently discontinued from IP:

- QTc >530 msec
- Increase in QTcF or QTcB by more than 60 msec compared to baseline on two separate ECG tracings.

5.4.4. Other Stopping Criteria

Subjects should be permanently discontinued from IP if any of the following conditions are met:

- Serum creatinine: 0.5 mg/dL increase from baseline, on 2 successive readings;
- eGFR of <60 on two consecutive readings using the CKD-EPI calculation (eGFR of <30 for moderate renal impairment);
- Peripheral neutropenia: absolute neutrophil counts <0.5 Gi/L on 2 successive assessments.

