4.1.1. Sentinel Cohorts with Enhanced Safety Monitoring

Sentinel cohorts with enhanced safety monitoring will be enrolled as part of a step-wise enrollment of subjects with different levels of renal impairment and disease severity (less severe and critically ill, Section 4.3). Subjects in the sentinel cohorts will have more stringent eligibility criteria (baseline creatinine clearance criteria and exclusion of subjects with diabetes mellitus and chronic kidney disease). The IV DNX formulation developed for this study contains 750 mg β -Cyclodextrin Sulfobutylether (SBE- β -CD, Captisol) per 50 mg of GSK1325756 (free base equivalent [FBE]), to achieve the desired

[figure not shown]
5mg/mL concentration (FBE) and ensure DNX remains in solution when added to the IV saline bag. Captisol is renally cleared with the potential for accumulation in subjects with severe renal impairment. As such, this study includes enhanced monitoring to evaluate for renal function. Subjects in the sentinel cohorts will undergo serum creatinine, eGFR and urine output assessments twice a day for the treatment period. Additional enhanced monitoring will be based on disease severity, peripheral neutropenia and bacterial infections.

Approximately 30 subjects who are less severely ill and have baseline creatinine clearance within normal reference ranges (creatinine clearance ≥ 80 mL/min) will be enrolled in sentinel cohort 1 (Figure 1). The IDMC will first review available safety data after completion of the PT Day 3 visit, from approximately 10 subjects who are less severely ill and have normal renal function enrolled in sentinel cohort 1. Enrollment of subjects with normal renal function will continue during this review.

Following a review of all available data from the approximately 30 subjects in sentinel cohort 1, and an acceptable outcome from the IDMC, approximately 10 subjects with mild renal impairment, defined as baseline creatinine clearance of 50-79 mL/min will be enrolled in sentinel cohort 2, while continuing to enroll subjects with normal renal function in the study. At this stage, both less severely ill and the more critically ill subjects may be enrolled.

The IDMC will review the available safety data after completion of PT Day 3 from subjects in sentinel cohort 2 with mild renal impairment. Additional subjects with mild renal impairment will not be enrolled until the safety review is conducted by the IDMC, and the determination of an acceptable outcome.

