Following an acceptable outcome from the IDMC review of the subjects with mild renal impairment, further enrollment of subjects with mild renal impairment will resume and approximately 10 subjects with moderate renal impairment (defined as baseline creatinine clearance of 30-49 mL/min) will be enrolled in sentinel cohort 3. The IDMC will review the available safety data after PT Day 3 from subjects in sentinel cohort 3 with moderate renal impairment. Following an acceptable outcome from the IDMC review, additional subjects with moderate renal impairment may be enrolled in the study.

Figure 1 Enrollment and Evaluation in Sentinel Cohorts

NOTE: CrCL = creatinine clearance

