4.2. Treatment Arms and Duration

Subjects will be randomized in a 2:2:1 ratio to receive:

- 15 mg FBE IV DNX BID +75 mg OSV BID;
- 50 mg FBE IV DNX BID + 75 mg OSV BID; or
- IV DNX placebo BID + 75 mg OSV BID

Treatment duration will be up to 5 days ([Figure 2](#)). The investigator may elect to continue open-label oseltamivir treatment. If a subject is discharged from the hospital in less than 5 days, treatment with IV DNX will discontinue, irrespective of whether the investigator elects to continue oral OSV treatment at discharge. Follow up will continue until Day 45 for all subjects.

Figure 2 Study Schematic

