Renal Risk	
The IV formulation of DNX contains Captisol that is renally cleared and has a potential for accumulation in renally impaired patients.
 
Healthy volunteers have been dosed in a phase 1 study with an IV DNX formulation containing higher concentrations of Captisol with no safety concerns.
	
The study has intensive renal monitoring and stepwise inclusion of subjects with normal renal function followed by subjects with mild and then moderate renal impairment after review by an IDMC. The IDMC will include an ad hoc nephrologist member if there are 10 subjects across all treatment arms withdrawn due to the renal stopping criteria or if renal expertise is needed.
 
Subjects with CrCl <30 mL/min will be excluded from the study.
 
At the current doses, the Captisol concentrations in subjects with CrCl >30 mL/min are predicted to be below that obtained clinically with marketed Captisol containing IV voriconazole.

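### The CKD-EPI eGFR <60 stop lies inside the entry range for mild renal impairment, so eligible mild subjects can lose study drug permanently with no renal decline

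*Protocol*

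**What the plan says.** Section 5.4.4 lists three conditions, any one of which ends IP permanently. The renal ones are a creatinine rise of 0.5 mg/dL over baseline on two successive readings, and "eGFR of <60 on two consecutive readings using the CKD-EPI calculation (eGFR of <30 for moderate renal impairment". The first is relative to baseline; the second is an absolute level.

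Sections 4.1.1 and 5.1 set the renal bands by creatinine clearance: normal is 80 mL/min or more; "mild renal impairment, defined as baseline creatinine clearance of 50-79 mL/min will be enrolled in sentinel cohort 2"; "moderate renal impairment (defined as baseline creatinine clearance of 30-49 mL/min) will be enrolled in sentinel cohort 3". After the sentinel phase, all three bands are eligible above 30 mL/min. Section 4.6.1 adds: "Subjects with CrCl <30 mL/min will be excluded from the study".

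On monitoring, "Subjects in the sentinel cohorts will undergo serum creatinine, eGFR and urine output assessments twice a day for the treatment period". On gating, "Additional subjects with mild renal impairment will not be enrolled until the safety review is conducted by the IDMC", and the moderate cohort opens only "Following an acceptable outcome from the IDMC review of the subjects with mild renal impairment" (4.1.1). Neither the protocol nor the SAP gives an eGFR limit for mild impairment or an eGFR rule relative to baseline.

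**The concern.** The only relief from the <60 limit is for moderate impairment, so mild subjects fall under <60 although their entry range begins at 50. The limit cuts through the population it is applied to, and the ordering is inverted: worse baseline function gets the looser rule.

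The stake is exposure. With readings twice a day in the sentinel cohorts, a stable subject could meet the stop within about a day of a course of up to five days. Cohort 2 has about 10 subjects, and the Independent Data Monitoring Committee (IDMC) would judge mild impairment on data thinned at the lower end of the mild range, just before admitting subjects with worse function. Stops without decline would also mix with true renal signals and count toward the 10 withdrawals that bring a nephrologist onto the IDMC (4.6.1). That count is a prompt, not a halting rule. No bias in the efficacy comparison is claimed.

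**Working it through.** **Inputs.** Stopping limits: <60 by default, <30 for moderate (5.4.4). Entry bands: mild 50-79, moderate 30-49, normal 80 or more (4.1.1, 5.1). Cohort 2: about 10 subjects (4.1.1). Allocation: "Subjects will be randomized in a 2:2:1 ratio to receive" 15 mg, 50 mg or placebo (4.2). The plan gives no figure of its own to reproduce.

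**Assumption.** The documents give no relation between clearance and CKD-EPI eGFR, so let eGFR = r × clearance, with r varied from 0.8 to 1.2. A whole-number entry value c is already under the limit L when r × c < L, that is, c < L/r.

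| r | Mild, L = 60: c below | Mild values (of 30) | Moderate, L = 30: c below | Moderate values (of 20) |
|---|---|---|---|---|
| 0.8 | 75.0 | 25 | 37.5 | 8 |
| 0.9 | 66.7 | 17 | 33.3 | 4 |
| 1.0 | 60.0 | 10 | 30.0 | 0 |
| 1.1 | 54.5 | 5 | 27.3 | 0 |
| 1.2 | 50.0 | 0 | 25.0 | 0 |

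For normal function, a value of 80 falls under 60 only if r < 60/80 = 0.75, so none is affected over this range.

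An additive offset (eGFR minus clearance) gives the same picture. At -10, -5, 0, +5 and +10, the mild values already under 60 number 20, 15, 10, 5 and 0 of 30.

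**Fall needed to reach the limit, at r = 1.**

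- From 80: (80 - 60)/80 = 25.0%
- From 79: (79 - 60)/79 = 24.1%
- From 65: (65 - 60)/65 = 7.7%
- From 50-59: none
- From 49: (49 - 30)/49 = 38.8%

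The margin shrinks to nothing across the mild band, then jumps to its largest value at the top of the moderate band.

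**Cohort 2.** 10 × 4/5 = 8 on DNX, about 4 per dose. If a share p of mild subjects starts below 60, the chance that at least one of 10 does is 1 - (1 - p)^10: 65% at p = 10% and 89% at p = 20%. These shares are assumed.

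**Comparison with the other absolute stops.** Each lies beyond its entry limit:

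- ALT: entry up to 8×ULN, stop above 10×ULN (5.1, 5.4.2).
- QTc: excluded above 480 msec (500 with bundle branch block), stop above 530 (5.2, 5.4.3).
- Neutrophils: excluded below 1.0 Gi/L, stop below 0.5 (5.2, 5.4.4).
- Moderate impairment: entry from 30, stop below 30, on the two renal scales.

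Only the mild eGFR limit falls inside its own entry band, which suggests an omission rather than deliberate caution.

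**The case against.** The strongest reply concerns size. Entry and stopping use different measures, so an overlap at 50-59 is the result for r = 1 only. If eGFR runs about 20% (or about 10 units) above clearance, the overlap disappears. The counts are entry values, not expected patients. All of this stands: the text supports saying that such subjects can be stopped, not how many would be.

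The error is also in the cautious direction, and it is contained. Stopped subjects remain in follow-up (5.4.1), oseltamivir is not the product being stopped, and a placebo subject loses only saline. Mild enrolment pauses for unblinded review, so early stops would be seen; a nephrologist can join whenever needed (4.6.1); and sentinel cohorts exclude diabetes and chronic kidney disease (5.2), which may reduce cases. After the sentinel phase only daily creatinine is scheduled (7.1), so two readings in about two days assumes that eGFR is computed from each. These points limit the consequence but do not remove the mismatch. Nor can sites simply use discretion, since section 7 allows waivers only for immediate safety concerns.

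Caution about the renally cleared excipient does not explain the rule. The exposure prediction in 4.6.1 covers clearance above 30, and the protocol doses subjects at 30-49 under a <30 limit.

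Finally, the SAP synopsis records termination after 10 subjects, while cohort 2 needed review of about 30 from cohort 1. The rule therefore could not have affected mild subjects in this trial.

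**Conclusion.** The concern holds on the text: the limit lies inside the mild entry band and is looser for worse baseline function. At equality of the two measures, one third of the whole-number mild entry values (10 of 30) start under it; the assumed ratios give 25 down to 0. The share of real subjects is unknown. The practical harm is loss of DNX exposure in part of a small gating cohort, with stops that resemble renal events. There is no added drug risk. The SAP summary of halting criteria is not shown to be affected, because its note names only the creatinine rule. It should be corrected in the protocol as written and before the rule is used elsewhere.

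**What to change.** In 5.4.4, for mild impairment only, replace <60 with one of:

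- **(a), preferred:** a clinically set fall from the subject's own baseline CKD-EPI eGFR on two consecutive readings.
- **(b):** a limit at the lower entry bound, <50, which follows the pattern already used for moderate impairment.

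Under either, stop any subject at eGFR <30. Keep <60 for normal function, <30 for moderate, and the 0.5 mg/dL creatinine rule.

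With (a) and the floor, no stable mild value is at the limit for any r of 0.6 or more (30/50). The floor is needed because a generous allowed fall could pass below 30: at an illustrative 40%, 0.6 × r × c < 30 holds for 6 of 30 values at r = 0.9 and 13 at r = 0.8; at 25%, for none from r = 0.8 to 1.1. Option (b) is ready to use but incomplete: it clears all stable values only at r of 1.0 or more, leaving 6 at 0.9 and 13 at 0.8, and a subject entering near 50 has almost no margin.

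Two limits remain. Clearance and eGFR are different scales, so carrying 30 across as a floor is a conservative convention. At r below 1.0 some moderate values also start under <30; that limit is kept on safety grounds.

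The cost is one wording change plus, for (a), a clinical decision on the size of the fall. Baseline creatinine is already collected, so no assessments or patients are added. Stopping becomes slightly less conservative in mild impairment, bounded by the floor and the creatinine rule.

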5.5. Subject and Study Completion

A completed subject is one who has completed the Day 45 Assessment.

The end of the study is defined as the last scheduled procedure shown in the Schedule of Activities for the last participant in the trial globally.

Completion of the trial globally is required in order to provide sufficient subjects as defined in Section 9.2, Sample Size Considerations.

6. STUDY TREATMENT

6.1. Investigational Product and Other Study Treatment

The term ‘study treatment’ is used throughout the protocol to describe any combination of products received by the subject as per the protocol design. Study treatment may therefore refer to the individual study treatments or the combination of those study treatments.

Table 1 Characteristics of Study Treatments

	Study Treatment		
	GSK1325756	Placebo ¹	Oseltamivir ²
Product name: danirixin			
Formulation description:	A sterile lyophilized powder containing GSK1325756H (hydrobromide salt hemihydrate) equivalent to 50mg of free base along with Beta-cyclodextrin sulfobutylether (Captisol), mannitol, citric acid and sodium hydroxide		Capsule: Grey/light yellow containing pregelatinized starch, talc, povidone K30, croscarmellose sodium, and sodium stearyl fumarate Oral suspension: sorbitol, monosodium citrate, xanthan gum, titanium dioxide, tutti-frutti flavoring, sodium benzoate, saccharin sodium and water.
Dosage form:	Infusion	Infusion ¹	Capsules ²
Unit dose strength(s)/Dosage level(s):	15 mg FBE; 50 mg FBE	N/A	75 mg
Route of Administration	For IV infusion	For IV infusion	Oral
Dosing instructions:	250 mL infusion	250 mL infusion	Dosing as per Prescribing Instructions
Physical description:	lyophilized powder/cake contained in a 30mL vial.	Clear solution	Capsules: grey/light yellow hard gelatin capsules. "ROCHE" is printed in blue ink on the grey body and "75 mg" is printed in blue ink on the light yellow cap. For Oral Suspension: Supplied as a white powder blend in a glass bottle.

	Study Treatment		
Product name: danirixin	GSK1325756	Placebo ¹	Oseltamivir ²
Method for individualizing dosage:	Each vial is reconstituted with 9.5 mL water for injection and further diluted with saline for IV infusion	Saline for IV infusion ¹	Capsules. Available in blister packages of 10 Oral Suspension: After constitution, the powder blend produces a white tutti-frutti-flavored oral suspension. After constitution with 55 mL of water, each bottle delivers a usable volume of 60 mL of oral suspension equivalent to 360 mg oseltamivir base (6 mg/mL).

1 No vials of placebo to match IV DNX will be provided. A normal saline solution of matched volume will be prepared by unblinded personnel at the site to act as a placebo to DNX.
 
2 No oseltamivir capsules or powder for oral suspension will be provided. Sites will source the OSV locally and it will be provided open-label. OSV is manufactured by Roche Pharmaceuticals.
			

6.1.1. IV IP and OSV Administration

6.1.1.1. Preparation of IV IP for Infusion

Unblinded personnel should prepare the IV IP infusion (DNX or matching PBO). Complete details on preparation of IV DNX will be provided in the pharmacy manual. The unblinded personnel should prepare a normal saline (0.9% sodium chloride) infusion for placebo to match IV DNX.

6.1.1.2. Preparation of OSV at the site

Details on preparation of oral suspension if needed for patients who are unable to swallow the capsules are available in the manufacturers prescribing information.

6.1.1.3. Administration of IV IP

IP infusion should be administered at a constant rate over approximately 1 hour (e.g. at an infusion rate of 250 mL/hour for a 250 mL infusion volume). Infusions should be given approximately 12 hours apart. If the first infusion of the day is administered after 12 noon, the next dose should be administered the following morning.

6.1.1.4. Administration of OSV

OSV dose is 75 mg to be administered twice daily for subjects who are able to swallow intact capsules. Dose adjustments of OSV (ie renal dosing) may be made as indicated in the prescribing information. For subjects unable to swallow intact capsules, qualified personnel may compound the appropriate dose of oseltamivir by opening capsules and pouring the contents of the capsules into a suitable small amount of sweetened food product such as sugar water, chocolate syrup, cherry syrup, dessert toppings to mask the bitter taste. The mixture should be stirred and the entire contents given to the subject.

The mixture must be swallowed immediately after its preparation [[Tamiflu SPC, 2010](#)]. Alternatively, the contents of the capsules can be made into suspension as per Tamiflu Prescribing Information or standard site procedures for administration via mouth, nasogastric, nasojejunal or gastrostomy tube. If the first dose of the day is administered after 12 noon, the next dose should be administered the following morning.

6.2. Treatment Assignment

Study treatment in this protocol refers to the blinded investigational drug IV DNX, IV DNX placebo and the open label oral OSV. Subjects will be assigned to 15 mg FBE IV DNX, 50 mg FBE IV DNX or IV DNX Placebo, in accordance with the randomization schedule generated by Clinical Statistics, prior to the start of the study, using validated internal software.

A description of each regimen is provided in the table below:

Table 2 Treatment Regimens for Study 201023/DAHLIA

Treatment Arm	Sample Size per influenza season / study (3 influenza seasons)	Treatment Label	Treatment Regimen ^a
A	40/120	15 mg FBE DNX	15 mg FBE IV DNX given twice daily with 75 mg oral OSV given twice daily
B	40/120	50 mg FBE DNX	50 mg FBE IV DNX given twice daily with 75 mg oral OSV given twice daily
C	20/60	PBO	IV DNX placebo given twice daily with 75 mg oral OSV given twice daily

a. OSV dose adjustments may be made as indicated in the prescribing information.

Subjects will be randomized using the RAMOS NG system. This system will be used by the investigator or designee to register the subject.

Details of how to use the RAMOS NG system to register and randomize subjects is provided in the study reference manual (SRM).

Subjects meeting all eligibility criteria will be randomized 2:2:1 to one of three treatment groups in accordance with the central randomization schedule generated by Clinical Statistics prior to the start of the study, using validated internal software. Minimization criteria will be based on influenza medication prior to hospitalization (Relenza, Tamiflu, peramivir or other), number of days of symptoms prior to hospitalization (0-3, 4-6), subject origin prior to hospitalization (nursing home, rehabilitation unit, home).

All randomized subjects will take investigational drug or matching placebo twice daily for up to 5 days in the hospital.

Once a randomization number has been assigned, it must not be re-assigned.

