- 6. Onset of influenza symptoms within 6 days prior to study enrolment. Symptoms may include cough, dyspnea, sore throat, feverishness, myalgias, headache, nasal symptoms (rhinorrhea, congestion), fatigue, diarrhea, nausea and vomiting.
- 7. A positive result from a rapid influenza test (provided by GSK) or other available, local laboratory diagnostic test;
- 8. Baseline renal criteria as follows:

Sentinel Cohorts:

- Normal renal function: Baseline creatinine clearance within normal reference ranges (≥ 80 mL/min) for the first approximately 30 subjects enrolled;
- Mild renal impairment: Baseline creatinine clearance of 50-79 mL/min for the next approximately 10 subjects enrolled into the sentinel cohort;
- Moderate renal impairment: Baseline creatinine clearance of 30-49 mL/min for the next approximately 10 subjects enrolled into the sentinel cohort.

Post-sentinel cohorts:

- Normal renal function, mild or moderate renal impairment: creatinine clearance > 30 mL/min.

9. Baseline Liver Function Tests as follows:

Liver parameter	ALT \leq 5xULN	ALT $>$ 5 and \leq 8xULN	ALT $>$ 8xULN
Bilirubin \leq 2x ULN	Include	Include only if bilirubin $<$ 1.5xULN	Exclude
Bilirubin $>$ 2x ULN	Exclude	Exclude	Exclude

SEX

10. Male or Female subjects could be eligible if :

Males:

Male subjects with female partners of child bearing potential must comply with the

following contraception requirements from the time of first dose of study medication until at least 36 hours (five half-lives) after the last dose of study medication.

- a. Vasectomy with documentation of azoospermia.
- b. Male condom plus partner use of one of the contraceptive options below:
 - Contraceptive subdermal implant
 - Intrauterine device or intrauterine system
 - Oral Contraceptive, either combined or progestogen alone [[Hatcher, 2007a](#)]
Injectable progestogen [[Hatcher, 2007a](#)]
 - Contraceptive vaginal ring [[Hatcher, 2007a](#)]
 - Percutaneous contraceptive patches [[Hatcher, 2007a](#)]

This is an all-inclusive list of those methods that meet the following GSK definition of highly effective: having a failure rate of less than 1% per year when used consistently and correctly and, when applicable, in accordance with the product label. For non-product methods (e.g., male sterility), the investigator determines what is consistent and correct use. The GSK definition is based on the definition provided by the ICH [[ICH, M3 \(R2\) 2009](#)].”

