5.2. Exclusion Criteria

A subject will not be eligible for inclusion in this study if any of the following criteria apply:

CONCURRENT CONDITIONS/MEDICAL HISTORY (INCLUDES LIVER FUNCTION AND QTc INTERVAL)

1. Subjects who, in the opinion of the investigator, are not likely to survive the next 48 hours beyond Baseline;
2. Immunosuppression, whether due to primary immunosuppressive conditions, such as history of inherited immunodeficiency syndromes, HIV infection, or secondary conditions, such as immunosuppressive medication, stem cell or solid organ transplantation, or malignancy;
3. Documented current liver disease (including Hepatitis A, B, or C), or known hepatic or biliary abnormalities (with the exception of Gilbert's syndrome or asymptomatic gallstones);
4. QTc Criteria: QTcB or QTcF >480 msec or >500 msec with bundle branch block;
5. For subjects enrolled in the sentinel cohorts: diabetes mellitus and chronic kidney disease;
6. Subjects who require dialysis, or are on renal replacement therapies;
7. Subjects who require extra corporeal membrane oxygenation (ECMO) at baseline (enrolled subjects who subsequently require ECMO may continue in the study)
8. Women who are pregnant as determined by a positive human chorionic gonadotrophin (hCG) ultrasensitive test prior to dosing or women who are

breastfeeding;

CONCOMITANT MEDICATIONS

9. Subjects who received other treatments for influenza including vitaglutam, umifenovir, and neuraminidase inhibitors (oseltamivir, zanamivir, peramivir) for more than 72 hours during current acute illness;
10. Subjects who received any immunoglobulins within 6 months of screening or planned administration of any of these products during the treatment period.
11. Subjects treated with cytotoxic or immunosuppressive drugs within six months of study enrolment. Topical, intra-articularly injected, or inhaled glucocorticoids, topical calcineurin inhibitors or imiquimod are allowed.

RELEVANT HABITS

12. Known history of drug abuse within 6 months of study start.

CONTRAINDICATIONS

13. History of sensitivity to any of the study medications, or components thereof or a history of drug or other allergy that, in the opinion of the investigator or Medical Monitor, contraindicates their participation.

DIAGNOSTIC ASSESSMENTS AND OTHER CRITERIA

14. Absolute neutrophil count <1.0 Gi/L

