7.2. Critical Baseline Assessments

- Demographic parameters to be collected include: year of birth, sex, race and ethnicity. Date and primary reason of hospitalization (influenza or not influenza related) will be recorded and if applicable, the date of intubation.
- Nasal swabs or nasopharyngeal sample will be taken for confirming an influenza infection. A rapid diagnostic influenza test will be provided by GSK or other local, validated laboratory test for influenza can be used.
- Vital signs to include temperature, heart rate, systolic and diastolic blood pressure, respiration rate, oxygen saturation. Oxygen delivery and ventilation status to be recorded approximately within approximately 1 hour prior to administration of the first dose of study medication;
- Influenza symptoms will be assessed at baseline prior to administration of study treatments. The presence of the following symptoms will be recorded: nasal symptoms (rhinorrhea, congestion), feverishness, cough, myalgias, fatigue, diarrhea, dyspnea, headache, sore throat, nausea and vomiting. The date of first onset of influenza like symptom(s) will also be recorded. The investigator or designee will assess and record influenza symptoms based on interview with the subject. In situations when subjects may not be able to communicate their symptoms, for example in subjects ventilated and/or sedated, the investigator or designee will record those signs/symptoms as ‘unable to assess’;
- Cardiovascular medical history/risk factors (as detailed in the CRF) will be assessed at baseline.
- Medical/medication/family history will be assessed as related to the inclusion/exclusion criteria listed in Section 5.
- Chronic underlying illness (including but not limited to asthma, COPD, diabetes, hypertension, Congestive Heart Failure) will be recorded.
- Pre-morbid functional status (defined as the best functional status in the 4 weeks prior to enrolment) and status at Baseline as measured by the Katz ADL scale and activity level (bed rest, limited ambulation or unrestricted) will be recorded in the eCRF. For subjects unable to communicate their pre-morbid functional status, this information should be requested from another close member of the household, close family member, or the subject’s regular physician (if the subject has been under the care of a single physician for 3 months or longer).
- Laboratory evaluations:

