9.4.1.3. Subgroup Analyses

To evaluate the benefit of DNX in a sub-population, one key subgroup has been pre-specified for evaluation of efficacy.

- **Disease severity at baseline:** Patients requiring CPAP (i.e. new use for respiratory distress and not for chronic purposes such as sleep apnea), BIPAP, mechanical ventilation, those who have hemodynamic instability (with or without pressor support), or have central nervous system involvement (eg encephalopathy, encephalitis) are considered a more severe population.

Additional subgroups will be pre-specified in the reporting analysis plan.

The KM estimates for the primary analysis and key secondary analyses will be repeated by the subgroups.

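### Baseline severity is not a minimisation factor, although control median TTCR is 5.8 v 20.1 days by severity: the cost is avoidable chance imbalance, modest beside sampling error and cheap to reduce

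*Protocol*

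**What the plan says.** **Allocation.** Protocol 6.2 randomises 2:2:1 and names three factors: "Minimization criteria will be based on influenza medication prior to hospitalization (Relenza, Tamiflu, peramivir or other", then "number of days of symptoms prior to hospitalization (0-3, 4-6), subject origin prior to hospitalization (nursing home, rehabilitation unit, home". Severity is not among them, and no other section of the protocol or SAP stratifies on it.

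**Severity elsewhere in the plan.** Inclusion criterion 4 describes less severe and critically ill subjects at enrolment. Critically ill enrolment opens after the committee reviews about 30 less severe subjects (4.1.1, 4.1.2): "At this stage, both less severely ill and the more critically ill subjects may be enrolled". Table 8 gives oseltamivir medians of 5.8 and 20.1 days. Section 9.4.1.3 says that "one key subgroup has been pre-specified for evaluation of efficacy", and that subgroup is disease severity at baseline. The primary model (9.4.1.1, Appendix 9) has a single exponential control hazard and a log hazard ratio per dose, with no covariate.

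**Time points.** Inclusion criterion 6 is "Onset of influenza symptoms within 6 days prior to study enrolment". Exclusion criterion 9 bars other influenza treatment, including neuraminidase inhibitors, only when taken "for more than 72 hours during current acute illness", whether or not the subject was in hospital. Section 7.2 adds: "Date and primary reason of hospitalization (influenza or not influenza related) will be recorded".

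**Status.** SAP 2.1 reports that the trial stopped after 10 subjects and is analysed descriptively. SAP 11.9 assesses no subgroups.

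**The concern.** Balancing factors should be the baseline variables most likely to move the primary endpoint. The one variable for which the plan documents a large effect on TTCR is left out.

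The control arm is one fifth of the trial: 20 of 100 subjects at the first planned look and 60 of 300 at the end. Because the model has no severity term, any chance excess of critically ill subjects in one arm is read as treatment effect. It then feeds the rules in Appendix 9: drop an arm or stop for futility below 30% probability of success, stop for success above 90%, and claim evidence of efficacy at the end above 50%.

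The two clinical factors that are used also stop at admission. A subject admitted on symptom day 2 and enrolled on day 6 is balanced as 0-3 days. A subject given 60 hours of oseltamivir in hospital before randomisation, and none before admission, is not counted as treated.

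**Working it through.** **Inputs.** Medians 5.8 and 20.1 days (Table 8). Arm sizes 20 v 40 and 60 v 120, control v one DNX arm (Table 2). Follow-up to Day 45 (4.2). First 30 or so subjects less severe (4.1.1, 4.1.2). Share of critically ill subjects: not given, so assumed at 10-40% overall.

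**Step 1: the plan's own figures.** A hazard of 0.83 per week gives a median of 7 × ln 2 / 0.83 = 5.85 days, matching the stated 5.8. The ratio of medians is 20.1 / 5.8 = 3.47. For the design as a whole, with one homogeneous population, a Monte Carlo approximation (normal posterior, the stated priors, looks at 100/200/300) gives type I error of 9.5-9.7% and power of 83.6-83.9% if the future study has about 300 events. The plan states 9% and 82%. If all 600 future subjects have an event, the results are about 20% and 91-92%. The plan does not state the event count; 300 is used below because it comes closest to Table 12.

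**Step 2: what imbalance does to the fitted hazard ratio.** Daily hazards are ln 2 / 5.8 = 0.1195 and ln 2 / 20.1 = 0.0345. The chance of response by day 45 is 1 − exp(−45 × hazard) = 0.995 and 0.788. Expected time at risk is that chance divided by the hazard: 8.33 and 22.85 days. With a fraction q critically ill, the single-hazard model estimates

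r(q) = [(1−q) × 0.995 + q × 0.788] / [(1−q) × 8.33 + q × 22.85].

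This gives r(0.4) = 0.0645, r(0.3) = 0.0736 and r(0.2) = 0.0849. At a true HR of 1, 40% critically ill on control against 30% on DNX looks like 0.0736 / 0.0645 = 1.14; 40% against 20% looks like 0.0849 / 0.0645 = 1.32.

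**Step 3: imbalance alone.** About 30 less severe sentinel subjects split 6 control and 12 per DNX arm. That leaves 14 v 28 at the first look with share p/0.7, and 54 v 108 at the end with share p/0.9. Binomial counts (400,000 draws) are put through r(q). **Step 4: imbalance plus sampling error.** Individual exponential times are simulated at true HR 1 (60,000 trials), with severity left to chance or fixed equal across arms. Each cell is the chance that the HR is at least 1.2 or at most 1/1.2.

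| Overall critically ill share p | 20 v 40: imbalance alone | total, unbalanced | total, balanced | 60 v 120: imbalance alone | total, unbalanced | total, balanced |
|---|---|---|---|---|---|---|
| 10% | 16% | 56% | 52% | 2% | 31% | 26% |
| 20% | 25% | 58% | 52% | 5% | 33% | 27% |
| 30% | 24% | 58% | 53% | 6% | 34% | 27% |
| 40% | 21% | 57% | 53% | 5% | 34% | 27% |

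**Step 5: decision error rates.** This is the Step 1 approximation with 300 future events, the same HR in both severity groups, and severity drawn for every subject. The sentinel rule is not imposed, which slightly overstates imbalance at the first look.

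| Share | Type I, unbalanced | Type I, balanced | Power (HR 1.2/1.5), unbalanced | Power, balanced |
|---|---|---|---|---|
| 10% | 11.6% | 8.8% | 74% | 77% |
| 20% | 12.0% | 8.1% | 68% | 72% |
| 30% | 11.1% | 7.6% | 65% | 69% |
| 40% | 10.6% | 7.0% | 63% | 67% |
| 50% | 9.7% | 6.7% | 62% | 65% |

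With 600 future events, type I error is higher throughout (17.7-21.4% unbalanced, 13.8-18.3% balanced), but the change from balancing is again about 3-4 points.

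**The case against.** **Randomisation is valid without this factor.** That stands. Severity imbalance is random in direction, so a reader who infers systematic bias goes further than the documents allow.

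**Ordinary sampling error dominates.** That stands too. With severity perfectly balanced, a null HR still falls outside 1/1.2 to 1.2 in about half of trials at 20 v 40. If severity is drawn for every subject and nobody is censored, imbalance alone gives 25-31% at the first look and 5-8% at the end. Those figures are tempting to quote as the harm, but they ignore the sentinel rule and Day 45, and they are not the gain from balancing.

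**The time-point mismatch has no shown consequence.** The documents give no effect of symptom duration or prior antiviral use on TTCR, so nothing supports saying that these drive it. A reader might also think that hospital-acquired influenza fits no printed level. It has zero symptom days before admission and codes as 0-3; the factor is uninformative for such a subject, not missing.

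**Interim decisions are not mechanical.** Sections 4.1 and 12.9.4 have the TTCR rule considered alongside other efficacy, PK, biomarker and safety data. This softens the effect on decisions but does not remove the imbalance from the TTCR input.

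**No rule was applied.** With 10 subjects, no formal interim and a descriptive SAP, the reported analysis is unaffected.

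**Conclusion.** The omission of severity is a real and avoidable weakness of the planned allocation. Its size is moderate. Balancing severity would remove about 4-6 percentage points of misleading hazard ratios at the first look and 5-7 at the end. In the approximate simulation it would lower type I error by about 3-4 points, from about 10-12% to 7-9% against the plan's limit of under 10%, and raise power by about 3-4 points.

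These figures rest on an assumed critically ill share (10-40%, or 10-50% for the error rates), exponential times with the Table 8 medians, an HR common to both severity groups and, for the error rates, about 300 future events. They do not show that the stated 9% and 82% are wrong: the future event count is not given and the simulation is approximate. Most of the power lost in a mixed population comes from censoring and the single-hazard model, which allocation alone does not cure.

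The mismatch between admission and enrolment is a secondary point. It is clear in the text, but it has no documented effect on TTCR.

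**What to change.** In Protocol 6.2:

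- Add baseline severity as a minimisation factor from the time critically ill enrolment opens. Use the definition in 9.4.1.3. The classes in 4.3 are expressly not exhaustive, and that section also gives a second, different list for the more severe population.
- Count symptom days (0-3, 4-6) from onset to randomisation.
- Count influenza antiviral use in the current illness up to randomisation, and print a level for none.
- Keep subject origin. Hospital discharge is itself a TTCR event (Table 5), so where a subject can be discharged to may matter, and nothing in the documents supports removing it.

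**Cost.** A wording change, reconfiguration of the randomisation system and one more entry at registration. The inputs are already collected: severity at entry, symptom onset date at baseline (7.2), and influenza medication from Day -7 where available (Table 3, footnote i). Dose, schedule and clinical management do not change.
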